## **6.5. Assessments (Table 3):**

### **6.5.a. Safety.**

- Vitals. Blood pressure, pulse, and temperature will be obtained at the beginning of every study visit.

Blood chemistry. Blood samples will be collected and used for comprehensive metabolic panel (CMP), complete blood count (CBC), lipid panel, and high sensitivity C-reactive protein (hs-CRP) at baseline and subsequent in-person visits. In case the initial tests are inconclusive or if further analysis is required, the participants may be asked to return for an additional blood draw.

- Adverse events. Participants will be queried about adverse events at every follow-up, including quarterly phone calls and follow-up visits.
- Medical history will be evaluated at screening and updates will be obtained at every visit thereafter.

**6.5.b. Adherence to supplementation protocol.** Remaining capsules will be counted at every follow-up. Adherence will be quantified as the percentage of capsules taken out of those dispensed.

**6.5.c. Common Data Elements (CDEs).** Key sociodemographic characteristics will be obtained at the Screening Visit (e.g., age, sex, race and ethnicity, income).

**6.5.d. Anthropometrics.** Height and weight will be obtained and used to calculate body mass index ( $\text{kg}/\text{m}^2$ ). Height will only be measured at baseline. Weight and waist circumference will be measured at every study visit.

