| Common Data Elements (CDEs)                                       | X                    |                         |                               |                           |                             |                          |
| Pain history  | X                    |                         |                               |                           |                             |                          |
| Michigan Body Map   | X                    |                         |                               |                           |                             | X                        |
| Graded Chronic Pain Scale-Revised (GCPS-R)                        | X                    | X                       |                               | X                         |                             | X                        |
| Western Ontario and McMaster Universities Arthritis Index (WOMAC) |                      | X                       |                               | X                         |                             | X                        |
| PainDETECT  |                      | X                       |                               |                           |                             | X                        |
| Patient Global Impression of Change (PGIC)                        |                      |                         | X                             | X                         | X                           | X                        |
| Medicine Acceptability Questionnaire (MAQ)                        |                      |                         |                               | X                         |                             | X                        |
| Pepper Assessment Tool for Disability (PAT-D)                     |                      | X                       |                               | X                         |                             | X                        |
| Fear Avoidance Beliefs Questionnaire (FABQ)                       |                      | X                       |                               |                           |                             | X                        |
| Pain Self-Efficacy Questionnaire (PSEQ)                           |                      | X                       |                               |                           |                             | X                        |

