#### **6.5.k. Other.**

- Acceptance of the intervention will be assessed with the Patient Global Impression of Change (PGIC) and the Medicine Acceptability Questionnaire (MAQ).
- Mood/affective factors will be assessed with the Fear Avoidance Beliefs Questionnaire (FABQ), Pain Self-Efficacy Questionnaire (PSEQ), Perceived Stress Scale (PSS), and the Geriatric Depression Scale-Short Form (GES-S).
- The Brief Pittsburg Sleep Quality Index (B-PSQI) will be used to assess sleep quality.

- Quality of life (QoL) will be assessed with the EuroQol 5 Dimension 5 Level (EQ-5D-5L).

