**6.5.I. Sample size and statistical approach:** This pilot study is designed as a small-scale test to guide the design and implementation of large-scale studies to evaluate the effectiveness of krill oil supplementation among older adults with chronic musculoskeletal pain. We will enroll 40 older adults who will be randomly assigned (1:1) to either krill oil ( $n=20$ ) or placebo ( $n=20$ ) for a 3-month trial duration. Approximately 16 participants per group after a 20% loss to follow-up is expected to provide sufficient data to indicate the feasibility of a larger study and to provide descriptive estimates of effects. **Aim 1.** Feasibility and acceptability will be determined as (1) meeting at least 80% of the recruitment goal ( $n=32$ ), (2) no more than 20% attrition, and (3) treatment acceptance and adherence ( $\geq 70\%$  consumption of prescribed doses and increased blood  $\omega$ -3 index). **Aim 2.** Mean changes in  $\omega$ -3 index and  $\omega$ -6: $\omega$ -3 ratio will be evaluated with paired-samples T-tests for within-group difference and independent-samples T-tests for between-group difference. An intention-to-treat approach will be used for between-group analyses. While there is currently no guidance on what may constitute a minimal clinically meaningful change in plasma  $\omega$ -3 index, current evidence supports that an  $\omega$ -3 index  $\geq 8\%$  may be protective against cardiovascular disease whereas an index of  $\leq 4\%$  indicates increased risk. Similarly, an  $\omega$ -6: $\omega$ -3 ratio of 4:1 or lower is considered optimal for health. Baseline and 3-month levels of the  $\omega$ -3 index and the  $\omega$ -6: $\omega$ -3 ratio will be compared against these benchmarks. **Aim 3.** Due to the repeated-measures design, we will use mixed-effects linear regression models to evaluate changes in pain intensity and functional interference (WOMAC), as well as changes in objective measures of physical function (SPPB, 6MWT). Fixed effects will be specified for the treatment group, time (in weeks), and a group\*time interaction effect. An independence covariance matrix structure will be assumed with a random intercept for each participant included. A 20% pain reduction on a 0-10 numeric rating scale is considered a clinically significant pain reduction. A 1-point change in the SPPB and a 50-m increase in the 6MWT are considered clinically meaningful changes for older adults.

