**6.6.d. Reporting of AEs/SAEs:** Study progress and safety will be reviewed bi-weekly or more frequently by the principal investigator. Progress reports, including AEs will be provided to an Independent Monitoring Committee for bi-annual reviews. The Independent Monitoring Committee for this study will consist of an established board that reviews all studies conducted within the University of Florida's Pepper Center during bi-annual conference calls. This board is comprised of (1) [name]., Chair, epidemiologist, (2) [name]., biostatistician, and (3) [name]., physician/clinical researcher. An annual report will be compiled and will include a list and summary of AEs, and whether adverse event rates are consistent with pre-study assumptions.

The PI will immediately report to the sponsor any SAE, whether or not considered study intervention related, including those listed in the protocol, and must include an assessment of whether there is a reasonable possibility that the study intervention caused the event. All SAEs will be followed until satisfactory resolution or until the site investigator deems the event to be chronic or the participant is stable.

The study sponsor will be responsible for notifying the Food and Drug Administration (FDA) of any unexpected fatal or life-threatening suspected adverse reaction as soon as possible, but in no case later than 7 calendar days after the sponsor's initial receipt of the information. In addition, the sponsor must notify FDA and all participating investigators in an Investigational New Drug (IND) safety report of potential serious risks, from clinical trials or any other source, as soon as possible, but in no case later than 15 calendar days after the sponsor determines that the information qualifies for reporting.

**6.6.e. Reporting events to participants:** In the case that adverse events are identified from blood chemistry tests, participants will be immediately notified by the investigators.

**6.7. Participant discontinuation/withdrawal from the study:** Participants are free to withdraw from participation in the study at any time upon request. The investigators may discontinue or withdraw a participant from the study for the following reasons:

- Significant study intervention non-compliance
- If any clinical adverse event (AE), laboratory abnormality, or other medical condition or situation occurs such that continued participation in the study would not be in the best interest of the participant

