Krill Oil for Pain and Physical Function in Older Adults

NCT06580912

03/05/2025

Statistical Analysis Plan

Feasibility and acceptability will be determined as (1) recruitment of at least 80% of the target sample ($n=32$), (2) attrition rate $\leq 20\%$, and (3) adherence rate $\geq 70\%$ (based on capsule counts and intake diaries). Changes in fatty acid profile (i.e., omega-3 index) will be analyzed using mixed-effects linear regression models with fixed effects for treatment group, time (as categorical), and a group-by-time interaction. While there is currently no guidance on what may constitute a minimal clinically meaningful change in plasma ω -3 index, current evidence supports that an ω -3 index $\geq 8\%$ may be protective against cardiovascular disease, whereas an index of $\leq 4\%$ indicates increased risk⁽⁸⁸⁾. Given the pilot nature of the trial, analyses will emphasize estimation of between-group differences and corresponding 95% confidence intervals rather than formal hypothesis testing. Estimates of variability and feasibility metrics will be used to inform outcome selection and design considerations for future trials. Changes in pain intensity, pain interference, and physical function will be analyzed using mixed-effects linear regression models, with fixed effects for treatment group, time (as categorical), and a group-by-time interaction, adjusting for age, sex, and BMI. A random intercept will be included for each participant, assuming an independent covariance structure. A 20% pain reduction on a 0-10 numeric rating scale is considered a clinically significant pain reduction.¹ A 1-point change in the SPPB and a 50-m increase in the 6MWT are considered clinically meaningful changes for older adults.² All analyses will follow an intent-to-treat approach, including all randomized participants in the groups to which they were assigned, regardless of adherence. A per-protocol analysis may also be conducted as a sensitivity analysis, including only participants with $\geq 70\%$ adherence. Missing data will be addressed using maximum likelihood estimation within the mixed-effects models, which accommodates data missing at random. Sensitivity analyses may be conducted using multiple imputation if warranted.

References

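### No exit capsule count or acceptability questionnaire is planned, and no rule says how leavers enter the 70% adherence criterion, so adherence and MAQ results are likely to be biased upward

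*Protocol*

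**What the plan says.** **Criterion.** Aim 1 sets three feasibility conditions: recruitment, attrition, and acceptance with adherence. Adherence means at least 70% of prescribed doses plus a rise in the omega-3 index. Table 1 lists 70% adherence as a primary endpoint.

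**Adherence measurement.** Section 6.5.b says "Remaining capsules will be counted at every follow-up" and divides capsules taken by capsules dispensed. Table 3 marks capsule count and dispensation at Baseline, Midpoint (week 6) and Final (week 12), and at neither phone contact. The omega-3 blood spot follows the same three visits. The SAP adds intake diaries as a source; no protocol section or Table 3 row collects them.

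**Acceptability measurement.** Section 6.5.k says "Acceptance of the intervention will be assessed with the Patient Global Impression of Change" (PGIC) and the MAQ. Table 3 marks the PGIC at the Q1 calls (weeks 1 to 4), Midpoint, Q3 calls (week 9) and Final. It marks the MAQ at Midpoint and Final only.

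**Leaving.** Section 6.7 says "Participants are free to withdraw from participation in the study at any time upon request" and lets investigators withdraw someone for significant non-compliance. It describes no exit visit, capsule return or exit questionnaire, and Table 3 has no column for one.

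**Analysis.** The SAP describes all analyses as "including all randomized participants in the groups to which they were assigned, regardless of adherence". Its missing-data methods are maximum likelihood within the mixed models and, if warranted, multiple imputation. No model is specified for adherence or the MAQ.

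**The concern.** Those who stop early are the participants most likely to have taken few capsules or to dislike the regimen, and the schedule gives them the fewest measurements. The statement that everyone randomized is analysed does not supply the missing counts, and the mixed models do not cover these outcomes. Section 6.7 strengthens the selection, because poor compliance can itself cause removal before the next count.

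The two definitions of adherence add to the problem. If the denominator is what was dispensed and counted, someone who takes every capsule to week 6 and then stops scores 100%. Against the 12-week prescription the same person scores 6/12 = 50%. So even leavers who do provide a count can raise the average.

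At stake are one primary feasibility criterion and the main acceptability instrument, which are meant to inform the decision on a larger trial. The optional per-protocol set is affected too: a leaver with no count cannot be classified as above or below 70%.

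**Working it through.** **Inputs from the documents**
- Enrolment: "We will enroll 40 older adults who will be randomly assigned (1:1) to either krill oil" (20) or placebo (20).
- Loss: "Approximately 16 participants per group after a 20% loss to follow-up". Check: 20 × (1 − 0.20) = 16 per group, 32 in all, so 8 leavers. This reproduces the plan's figure.
- Recruitment floor: "recruitment of at least 80% of the target sample". Check: 0.80 × 40 = 32, as stated.
- Attrition limit: no more than 20% in Aim 1 and the SAP, so 8 of 40 still passes. Table 1 writes it as below 20%, which allows 7.

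**Assumptions (the documents give no figures)**
- The 70% criterion is a mean over participants.
- Stayers average 80% or 75% of prescribed doses.
- Leavers average 0%, 25%, 40% or 50%. The value 50% corresponds to full adherence up to week 6.

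**Formula**
Mean over all randomized = (32 × stayers + 8 × leavers) / 40.

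| Stayers | Leavers 0% | 25% | 40% | 50% |
|---|---|---|---|---|
| 80% | 64% | 69% | 72% | 74% |
| 75% | 60% | 65% | 68% | 70% |

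Example: (32 × 80 + 8 × 25) / 40 = 2,760 / 40 = 69%.

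**Break-even leaver adherence for an overall 70%**
- Stayers at 80%: (40 × 70 − 32 × 80) / 8 = 240 / 8 = 30%.
- Stayers at 75%: (2,800 − 2,400) / 8 = 50%.

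**Fewer leavers**
With 4 leavers, stayers at 80% give at least 36 × 80 / 40 = 72%, so the criterion passes whatever the leavers did. Stayers at 75% give 67.5%, 70% or 72.5% for leavers at 0%, 25% or 50%. The problem shrinks as attrition falls.

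**If the criterion is instead a share of participants**
If 23 of 32 stayers reach 70%, the share is 71.9% among stayers. It is 23/40 = 57.5% if every leaver counts as a failure, and 28 adherent stayers would then be needed for 28/40 = 70%. The documents do not say which unit applies.

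**MAQ**
The plan sets no MAQ threshold, so no pass or fail can be computed. Only the likely direction can be stated.

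**The case against.** The strongest reply is that the plan holds more data on leavers, and more protection, than the gap suggests. Much of this stands, and it rules out several stronger readings.

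- *Acceptability is measured only at weeks 6 and 12.* Not so. The PGIC is a named acceptance measure and is also collected at the Q1 and Q3 calls, so an early leaver may have one. It rates change, however, and the MAQ is the instrument dedicated to acceptability.
- *Leavers contribute no data.* Not so. Anyone who leaves after the week-6 visit has a count, an MAQ and a PGIC. Section 6.6.c.3 also records adverse events for 7 days (30 if serious) after participation ends.
- *The feasibility verdict comes from those who stay.* Not so. Recruitment counts everyone enrolled and attrition counts leavers directly, so widespread rejection of the capsules would show there. Attrition is a separate threshold, though: a trial can pass at 20% attrition and also pass adherence on stayers alone.
- *The plan restricts adherence to completers.* It does not say so, and the SAP wording points the other way. What is missing is the data and the rule needed to carry that wording out.

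The SAP's intake diaries could close part of the adherence gap, but no collection is described. Finally, treating every non-returner as non-adherent would penalise the same people under both attrition and adherence, and would read withdrawals unrelated to the product as rejection. That objection is fair, so such a rule belongs in a sensitivity analysis.

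**Conclusion.** The concern holds for the adherence criterion and the MAQ, and for nothing wider. After dispensing, both are scheduled only at weeks 6 and 12, no exit assessment is described, and no rule places leavers or unreturned capsules in the 70% figure. Both results are likely to be biased upward, on the assumption that leavers adhere less and accept less than stayers.

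If 8 of 40 leave and the criterion is a mean, the adherence result falls from 80% to between 64% and 74%, or from 75% to between 60% and 70%, for leavers at 0% to 50%. Whether 70% is met can therefore depend on how leavers are counted. It need not: with stayers at 80%, leavers averaging 30% or more leave the criterion met, and so does any leaver adherence if only 4 leave. The adherence values are assumptions throughout. The change should still be made, because exit counts and questionnaires cannot reliably be recovered afterwards.

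**What to change.** 1. **Collect exit data.** Add an early-termination contact to Table 3 and section 6.7, by visit or by phone with mailed capsule return: capsule count, MAQ, PGIC, reason for stopping and adverse events. All but the reason for stopping already have a row in Table 3.
2. **Define the criterion.** In Aim 1 and the SAP, compute adherence as capsules taken out of the full 12-week prescription, for all randomized participants who were dispensed capsules. Say whether 70% refers to a mean or to a share of participants, and state in advance how the main analysis handles a participant whose capsules never come back.
3. **Add two sensitivity analyses.** One counts participants with no capsule return as non-adherent; the other uses attendees only.
4. **Reconcile the texts.** Section 6.5.b uses capsules dispensed, Aim 1 uses doses prescribed. Section 6.5.b has counts at every follow-up, a phrase that section 6.5.a uses to include phone calls, while Table 3 has counts at visits only. The SAP's intake diaries need a collection schedule or should be removed.

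Cost: wording in both documents and a short contact for about 8 people. The adherence and acceptability figures may be noticeably less favourable. Scoring against the full prescription also makes adherence overlap with attrition, which the report should say.

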**Table 3. Schedule of Activities**

| Procedures  | Screening            | Enrollment/
Baseline | Q1 Calls                      | Midpoint                  | Q3 Calls                    | Final                    |
|---|----------------------|-------------------------|-------------------------------|---------------------------|-----------------------------|--------------------------|
| Visit #
Week(s)
Duration                                    | 1
-4 to 1
1 hr | 2
1
2-3 hrs       | Phone
1-4 +/- 1
15 mins | 3
6 +/- 1
1.5-2 hrs | Phone
9 +/- 1
15 mins | 4
12 +/- 1
2-3 hrs |
| Informed consent   | X                    |                         |                               |                           |                             |                          |
| Randomization   | X                    |                         |                               |                           |                             |                          |
| Capsule count & dispensation                                      |                      | X                       |                               | X                         |                             | X                        |
| Health assessment  |                      |                         |                               |                           |                             |                          |
| Medical history/update  | X                    | X                       |                               | X                         |                             | X                        |
| Adverse events  |                      |                         | X                             | X                         | X                           | X                        |
| Vital signs   | X                    | X                       |                               | X                         |                             | X                        |
| Anthropometrics  |                      |                         |                               |                           |                             |                          |
| Height  | X                    |                         |                               |                           |                             |                          |
| Weight  | X                    | X                       |                               | X                         |                             | X                        |
| Waist circumference   |                      | X                       |                               | X                         |                             | X                        |
| Physical Performance                                       |                      |                         |                               |                           |                             |                          |
| Short Physical Performance Battery (SPPB)                         | X                    |                         |                               | X                         |                             | X                        |
| Handgrip strength   |                      | X                       |                               |                           |                             | X                        |
| 6-minute walk test (6MWT)   |                      | X                       |                               |                           |                             | X                        |
| Whole blood collection                                     |                      | X                       |                               | X                         |                             | X                        |
| Dried blood spot (OmegaQuant)                                     |                      | X                       |                               | X                         |                             | X                        |
| CMP, CBC (safety), lipids, hs-CRP                                 |                      | X                       |                               | X                         |                             | X                        |
| Inflammatory markers (IL-6 and TNF- $\alpha$ )                    |                      | X                       |                               |                           |                             | X                        |
| Questionnaires   |                      |                         |                               |                           |                             |                          |
| Common Data Elements (CDEs)                                       | X                    |                         |                               |                           |                             |                          |
| Pain history  | X                    |                         |                               |                           |                             |                          |
| Michigan Body Map   | X                    |                         |                               |                           |                             | X                        |
| Graded Chronic Pain Scale-Revised (GCPS-R)                        | X                    | X                       |                               | X                         |                             | X                        |
| Western Ontario and McMaster Universities Arthritis Index (WOMAC) |                      | X                       |                               | X                         |                             | X                        |
| PainDETECT  |                      | X                       |                               |                           |                             | X                        |
| Patient Global Impression of Change (PGIC)                        |                      |                         | X                             | X                         | X                           | X                        |
| Medicine Acceptability Questionnaire (MAQ)                        |                      |                         |                               | X                         |                             | X                        |
| Pepper Assessment Tool for Disability (PAT-D)                     |                      | X                       |                               | X                         |                             | X                        |
| Fear Avoidance Beliefs Questionnaire (FABQ)                       |                      | X                       |                               |                           |                             | X                        |
| Pain Self-Efficacy Questionnaire (PSEQ)                           |                      | X                       |                               |                           |                             | X                        |
| EuroQol 5 Dimension 5 Level (EQ-5D-5L)                            |                      | X                       |                               |                           |                             | X                        |
| Brief Pittsburg Sleep Quality Index (B-PSQI)                      |                      | X                       |                               | X                         |                             | X                        |
| Perceived Stress Scale (PSS)                                      |                      | X                       |                               |                           |                             | X                        |
| Geriatric Depression Scale-Short Form (GDS-S)                     |                      | X                       |                               |                           |                             | X                        |
| Diet assessment (DHQ-III)   |                      | X                       |                               |                           |                             | X                        |
| Montreal Cognitive Assessment (MoCA)                              | X                    |                         |                               | X                         |                             | X                        |
| NIH Toolbox   |                      | X                       |                               |                           |                             | X                        |

**6.5.e. Biological specimen collection and laboratory evaluations.** Whole blood samples will be collected to assess the following:

- **Omeqas 3 & 6 profile:** Analysis of essential fatty acids will be conducted at baseline, 6 weeks, and 12 weeks with dried blood spots, as described elsewhere. Gas chromatography will be used to quantify 24 fatty acids, including 7  $\omega$ -6s and 4  $\omega$ -3s, from which the  $\omega$ -3 index and the  $\omega$ -6/ $\omega$ -3 ratio can be calculated. The CV for the dried blood spot  $\omega$ -3 index is <5%.

The omega-3 index, the percent of EPA+DHA of total fatty acids in erythrocytes, has been proposed as a more useful and clinically relevant biomarker of  $\omega$ -3 status. Although the  $\omega$ -6: $\omega$ -3 ratio has shown utility in chronic disease, it is limited by several theoretical and practical difficulties. Evidence suggests that much of the associations seen with the  $\omega$ -6: $\omega$ -3 ratio may be largely explained by the  $\omega$ -3 index. Moreover, the  $\omega$ -3 index is highly responsive to changes in EPA and DHA intake, making it a more useful marker of intake.

- Inflammatory markers: We will measure hs-CRP at baseline and 6- and 12-week follow-ups. We will also measure IL-6 and TNF- $\alpha$  from blood samples collected at baseline and 12-week follow-up.

